#### Experimental Procedures

Intake Session: After determining eligibility, participants will complete measures of social and psychological functioning (DERS, IRI, PANAS-2, TMS, AIHQ-A, NIH SRS, PHQ-9, BES, EMT, SIAS, PFQ) and the two laboratory emotion perception tasks (BLERT, EPBT) through an online Qualtrics survey on a standard desktop computer in the laboratory. At this time, they will provide four recent stressful experiences for the personalized stressor task.

Training Session: All participants will come back to their lab for this session (ideally between 5-7 days after the intake session), which will take approximately 1.5 hours. First, all participants will be asked about: 1) current distress and suicidal urges (i.e. Suicide Risk Protocol), 2) any changes in medications since the previous visit, 3) nicotine, caffeine, and alcohol use that day, 4) subjective units of general psychological distress (SUDS; visual analogue scale from 1-9), 5) dissociation state, assessed using self-report (Dissociative-Tension States Scale 4 item version-DSS-4 from the DSS-acute), 6) levels of arousal with the Sedation Scale, and 7) current affect with the PANAS-2. Then, the experimenter will affix electrodes and will use Biopac MP150 hardware and AcKnowledge software for data acquisition. All participants will be assessed for baseline negative emotional arousal with psychophysiological (galvanic skin response) measures for five minutes. Then, participants will be randomized to one of three groups:

Condition 1: Mindful Breathing. Participants assigned to this condition will first receive an orientation to mindful breathing, an emotion regulation skill based on Mindfulness Based Stress Reduction (Kabat-Zinn, 1990). The experimenter will orient them to the concept of focusing attention on the breath while feeling intense emotions, explaining that it's an active skill that one can use to calm down when distressed. After the initial orientation, participants are instructed to participate in the stressor task while practicing the mindful breathing skill. Reductions in emotional arousal will be continuously monitored using a real-time monitoring program that samples arousal through skin conductance every 500ms relative to the average baseline arousal. Emotional distress will also be assessed repeatedly throughout the task (SUDS). Once participants reduced their sympathetic arousal (returning to baseline in skin conductance) in the stressor task, a novel tone will be heard through the headphones. Through classical conditioning, participants learn to associate this specific sound with reductions in negative emotional arousal and distress.

Condition 2: Habituation. This comparison condition will most closely resemble the procedures of the previous study on generalizing emotion regulation (Pro00035922). Participants will hear each stressor for a minimum of 2 and a maximum of 4 times. Reductions in emotional arousal will be continuously monitored using a real-time monitoring program that samples arousal through skin conductance every 500ms relative to the average baseline arousal. Emotional distress will also be assessed repeatedly throughout the task (SUDS). Once participants reduced their sympathetic arousal (returning to baseline in skin conductance) in the stressor task, a novel tone will be heard through the headphones. Through classical conditioning, participants learn to associate this specific sound with reductions in negative emotional arousal and distress.

Condition 3: Control. This control condition will only present the stressor task without further instructions. Although emotional distress (SUDS) and sympathetic arousal (SCR) will be measured in this task as the first condition, participants in this condition will not hear the tones.

Immediately after the emotional stressor task, all participants will again report: 1) subjective units of general psychological distress (SUDS; visual analogue scale from 0-9), 2) dissociation state, assessed using self-report (Dissociative-Tension States Scale 4 item version-DSS-4 from the DSS-acute), 3) levels of arousal with the Sedation Scale, and 4) current affect with the PANAS-2. They will then complete the laboratory emotion perception bias task and a manipulation check. Afterward, they will be oriented to the mobile phone prompts they will receive during the testing phase.

Testing Phase: During the one-week testing phase, participants in both conditions will receive three text-message prompts through their own phones randomly each day. These prompts will function both as an EMA measurement of self-reported negative emotional distress, as well as the delivery method of the tones. We will have a specific application, processed and stored on Heroku, that will receive and send text messages to participants via Twilio. In each prompt, participants will be asked to report on their current negative emotional distress (SUDS). When participants report high distress (i.e.,  $SUDS > 2$ ), they will automatically hear the tone by receiving a text message with an .mp3 file. The participants in the control conditions will also hear the tone despite having no previous associations with it, to control for potential placebo effects. After hearing this sound, participants will report again on

their distress, then complete the phone-based emotion perception task. As a manipulation check, the participants in the emotion regulation intervention condition will be asked if they actually used the mindful breathing skill. If the participant does not meet criterion for high distress, they will instead receive a text response on their phone thanking them for their response (see text message sample script document).

All participants will complete the laboratory emotion perception tasks and self-report measures of emotion and psychological functioning through an online Qualtrics survey at the end of this testing phase. They will also complete an exit questionnaire through this Qualtrics survey (see exit questionnaire document).

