(3) A phone-based assessment of emotion perception, adapted from procedures used in text-based emotion perception research in healthy populations (Cheshin, Rafaeli, & Bos, 2011). Participants receive standardized text messages that are previously rated for emotional valence on a 0 (very negative) to 9 (very positive) scale by independent raters. To increase ecological validity, participants are told that these messages have been sent by the experimenter, who is expressing an emotion through the message (e.g. "I just got into an argument with a friend, so I'm not having a good day"). After participants receive the text message, they are instructed to rate the valence of the emotion of the message on the same 10-point scale. This phone-based emotion perception task will only be administered during the one-week testing phase. See the text message script document for the text message content participants would receive during testing phase.

Emotion: Emotional arousal will be measured through self-report and physiological measures: (1) Skin conductance will be measured using Ag-AgCl electrodes, which are connected to a Biopac MP150 device in an adjacent room. Amplified signals of analog data are converted to digital form and filtered using Biopac's Acqknowledge Software and are stored in a database on the computer. (2) Subjective units of general psychological distress (SUDS; visual analogue scale from 0-100); (3) the Sedation Scale (SS), a self-report measure of emotional and general levels of arousal, and (4) the PANAS-2 (Watson, Clark, & Tellegen, 1988), a measure of current emotional state.

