Specific Aim 1: Aim 1 will determine if the emotion regulation intervention leads to fewer negative biases in emotion perception during the laboratory training session. For this aim, we will conduct ANCOVA analyses to study group differences in performance on the emotion perception laboratory tasks, controlling for their baseline scores assessed in the intake session. To compare the conditions' impacts on negative biases, we will analyze group differences in 1) number of trials with neutral facial expressions are misclassified as negative emotions; 2) accuracy for positive emotions and negative emotional expressions. We will also examine the relationship between emotional distress and emotion perception. Hypothesis 1: Participants in our emotion regulation condition will have less negative bias in emotion perception (e.g. fewer neutral faces misclassified as negative, lower accuracy for negative emotions, higher accuracy for positive emotions) compared to participants in both the control conditions. Even though the perspective-taking and mindful breathing conditions may have similar effects (e.g. increasing attention to social cues (Olsson et al., 2016; Quaglia, Goodman, & Brown, 2016)), perspective-taking inductions may still lead to mood-congruent biases by increasing negative emotional responses (Lamm, Batson, & Decety, 2007). Therefore, we predict that the emotion regulation intervention would reduce this bias significantly more than both the worry and perspective-taking conditions. We also predict that intensity of emotional distress will be related to negative biases in emotion perception.

Specific Aim 2: Aim 2 will compare the changes in emotion perception over time between the emotion regulation breathing condition and the control conditions. For this aim, Multilevel modeling (MLM) will be used because it permits evaluation of longitudinal data on participants over time with trajectories for each participant examined as random effects. We will conduct MLM analyses to study group differences in changes in the laboratory emotion perception tasks assessed during intake (time 1), the training session (time 2) and after the testing phase (time 3). For the phone-based behavioral task, we will first examine the psychometric properties of this measure in this clinical sample. Then, we will analyze group

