differences in the valence of emotion perception ratings over the one-week testing phase. We will also examine whether changes in emotion dysregulation and distress mediate changes in negative biases over time. Finally, we will also explore the effects of the intervention on self-reported psychological and social functioning. Hypothesis 2: One week of hearing the tones via mobile phones will lead to greater long-term changes in negative biases emotion perception for participants in the emotion regulation condition compared to the participants in the control conditions. Changes in emotional regulation and distress over time will mediate changes in negative biases in emotion perception over time.

If our hypotheses are not supported and the conditions do not have significantly different effects on emotion perception, these findings would be indicative of trait-like deficits in emotion perception beyond the momentary effects of mood or perspective-taking. We would then use moderation analyses to explore the role of other stable factors within emotion perception performance, such as trait empathy (measured by the IRI) or psychiatric diagnoses.

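### Aim 2's phone ratings exist only at prompts where the pre-tone SUDS exceeds 2, so the between-arm comparison is conditional on post-randomisation distress

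*Combined protocol and SAP*

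**What the plan says.** Under Experimental Procedures, participants are randomised at the training session. The Testing Phase paragraph then gives three prompts a day for one week, so at most 3 x 7 = 21. Each prompt asks for current SUDS, and two branches follow:

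- **SUDS above 2:** "they will automatically hear the tone by receiving a text message with an .mp3 file". Participants then report again on "their distress, then complete the phone-based emotion perception task".
- **Otherwise:** "If the participant does not meet criterion for high distress, they will instead receive a text response on their phone thanking them".

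Measures and Tasks adds: "This phone-based emotion perception task will only be administered during the one-week testing phase". There is therefore no intake or training-session phone score.

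Data Analysis & Statistical Considerations, Specific Aim 2, opens its phone-task plan with "For the phone-based behavioral task, we will first examine the psychometric properties of this measure in this clinical sample" and then analyses group "differences in the valence of emotion perception ratings over the one-week testing phase". It does not mention the SUDS condition, unequal numbers of ratings by arm, or participants with no rating. Hypothesis 2 adds: "Changes in emotional regulation and distress over time will mediate changes in negative biases in emotion perception over time".

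The SUDS range is 0-100 in Measures and Tasks, and 1-9 and then 0-9 around the training-session stressor task. The range used on the phone is not stated.

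**The concern.** The first SUDS at a prompt decides whether an outcome exists. It is measured after randomisation, and distress is what the intervention is meant to reduce. If mindful breathing lowers distress at the moment a prompt arrives, that arm yields fewer ratings, taken from its remaining distressed moments and its more distressed people. Randomisation no longer protects the comparison, and any benefit that consists of having fewer distressed moments goes uncounted.

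The phone task is the only emotion perception measure sampled in daily life, which is the setting Aim 2 is about. The first SUDS as a mediator is also truncated for this outcome, because it exceeds 2 wherever a phone rating exists. A rating that was never requested cannot be recovered at analysis.

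**Working it through.** **The plan's own figure.** The only power statement concerns the primary bias outcome: 72 participants, f = 0.38, alpha 0.05. With noncentrality 72 x 0.38^2 = 10.40 and 2 and 69 degrees of freedom, power is 81.3%, which agrees with the stated minimum of 80%. It is not in question here. The plan gives no figure for the phone comparison.

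**Inputs.** From the protocol: the cut at 2, up to 21 prompts, and a rating scale where higher is more positive. Assumed, because the documents do not give them: pre-tone distress D normal with between- and within-person SD 1.5 each (variance 2.25 + 2.25 = 4.5, SD 2.12); control mean 2.5, 3.5 or 4.5; mindful breathing lowers the mean by 1 point; ratings fall 0.4 per distress point; all prompts answered.

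**Step 1: who is rated, and what is kept (no post-tone effect).** P(D > 2) = 1 - Phi((2 - mu)/2.12). The mean among triggered prompts is mu + 2.12 x phi(a)/(1 - Phi(a)), with a = (2 - mu)/2.12. The true distress difference is 1.0, so the triggered difference is the fraction kept.

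| Control mean | P(D > 2), control / mindful | Ratings per person (x 21) | Triggered mean, control / mindful | Kept, 0-9 SUDS |
|---|---|---|---|---|
| 2.5 | 0.593 / 0.407 | 12.5 / 8.5 | 3.89 / 3.52 | 0.364 |
| 3.5 | 0.760 / 0.593 | 16.0 / 12.5 | 4.37 / 3.89 | 0.479 |
| 4.5 | 0.881 / 0.760 | 18.5 / 16.0 | 4.98 / 4.37 | 0.613 |

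A simulated random-intercept analysis with 24 per arm agrees: 34%, 49% and 66% of the all-prompt difference.

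**Step 2: a 0-100 phone SUDS.** The cut becomes 2 x 9/100 = 0.18 on the 0-9 metric. The same formulas keep 0.588, 0.725 and 0.844.

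**Step 3: add an acute post-tone effect.** The condition uses the SUDS before the tone; the rating comes after it. Let the tone lower distress by a further 0.5 in mindful breathing at triggered prompts, worth 0.4 x 0.5 = 0.20 rating points. With shift s, all prompts give 0.4s + 0.20 x P(D > 2 in mindful breathing); triggered prompts give 0.4 x (difference in triggered means) + 0.20. At control mean 3.5:

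| Pre-tone shift | All prompts | SUDS > 2 only |
|---|---|---|
| 0 | 0.15 | 0.20 |
| 0.25 | 0.24 | 0.25 |
| 0.5 | 0.34 | 0.30 |
| 1 | 0.40 + 0.20 x 0.593 = 0.52 | 0.4 x 0.479 + 0.20 = 0.39 |

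For the 1-point shift, 0.39/0.52 is about 76%. The same calculation gives 0.35/0.48, about 72%, at control mean 2.5 and 0.45/0.55, about 81%, at 4.5. A separate simulation with rounded, bounded 0-9 scores and shifts of 0.5 to 1.5 kept 62-81%. Its reference let the drop act at every prompt, so its lower end is somewhat pessimistic. Without the acute effect it kept 37-58%.

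**Step 4: sensitivity.** With no arm difference in distress, the two analyses agree (0.01 and 0.01). An effect on ratings that bypasses distress is not attenuated (0.30 in both). In the separate simulation at control mean 3.5 and a 1-point shift, if people with high usual distress also rate more negatively for other reasons, 20% or less is kept and the sign can just reverse (-5%); the opposite correlation keeps 72%.

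**The case against.** The strongest reply is that the task is placed after the tone on purpose. The tone is conditioned to falling arousal, Hypothesis 2 concerns what the cues do, and the Aim 2 statement has the reminder followed by the tasks. Perception just after a cue is a legitimate target, and an effect acting only through the tone is not attenuated. With no pre-tone shift, rating every prompt would dilute it (0.15 against 0.20). This stands, so post-tone ratings deserve their own analysis. It does not rescue the present text, which describes the comparison as covering the week and never states the condition.

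A reader might infer more than the documents support:

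- **That the phone difference must shrink towards zero if mindful breathing works.** This needs a reduction in pre-tone distress carried over between prompts. The earlier study in Background & Significance reports that phone reminders reduced distress, but not whether the drop followed each tone or persisted to the next prompt.
- **That the mediation analysis fails altogether.** Only the first SUDS is truncated. The second SUDS can take any value, and the DERS does not depend on the cut.
- **That a null phone result alone leads to the conclusion that "these findings would be indicative of trait-like deficits in emotion perception".** That conclusion applies when the hypotheses are unsupported and the conditions do not differ on emotion perception, which includes laboratory tasks given to everyone.

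It is also fair to say that the comparison is weak either way. In the 24-per-arm simulation, two-arm power is only 26-29% with all prompts and 9-17% with triggered prompts. The text-message script is not among the documents and could show a different sequence.

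**Conclusion.** The point holds in a bounded form. As worded, phone ratings exist only where a post-randomisation, pre-tone SUDS exceeds 2, and the Aim 2 analysis neither says so nor allows for it. If mindful breathing lowers pre-tone distress, the comparison is not between groups as randomised and the part of the effect carried by that distress is attenuated.

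The size rests on assumptions about the distress distribution, the shift and the SUDS range, so only ranges can be given. About 36-61% is kept on 0-9 and 59-84% on 0-100 with a 1-point shift and no post-tone effect; about 62-81% is kept on 0-9 with an acute drop of 0.5; nothing is lost if the effect is purely post-tone. The laboratory tasks at all three time points, and the primary sample size, are untouched. This affects one Aim 2 outcome, but it is cheap to correct before data collection and cannot be corrected afterwards.

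**What to change.** Keep the tone trigger at SUDS > 2, but collect the phone rating at every answered prompt: after the tone and second SUDS when triggered, and with the thank-you text otherwise. Under Specific Aim 2:

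- use ratings from all answered prompts for the between-arm phone comparison;
- report post-tone ratings (SUDS > 2) separately, labelled as a conditional analysis of the immediate cue effect;
- tabulate by arm the prompts answered, prompts triggered and ratings obtained;
- state the phone SUDS range.

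The cost is one change to the message sequence and a few sentences. At an assumed control mean of 3.5 it adds 21 - 16.0 = 5.0 ratings per person over the week in control and 21 - 12.5 = 8.5 in mindful breathing. The downsides are this modest burden and the dilution of a purely acute tone effect in the all-prompt analysis, which the conditional analysis would still show.

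If the sequence cannot change, state under Specific Aim 2 that the phone comparison is conditional on post-randomisation distress and is not a randomised test of Hypothesis 2, and rest Hypothesis 2 on the time 3 laboratory tasks.

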## Selection of Subjects

Inclusion criteria include

- (1) ages 18-55;
- (2) have a smartphone and agree to receive text-messages;
- (3) high emotion dysregulation, assessed with the Difficulties with Emotion Regulation Scale (DERS)(Gratz & Roemer, 2004). There is no single consensus definition of difficulties with emotion regulation. However, one influential contemporary model proposes a multi-dimensional approach to conceptualizing difficulties with emotion regulation, including difficulties with: emotional awareness, emotional clarity, achieving goals when upset, impulsivity when upset, unwillingness to accept negative affect when upset, and accessing strategies to regulate emotions when upset (Gratz & Roemer, 2004). In the present application, we utilize this model and accompanying measure, the Difficulties with Emotion Regulation Scale (DERS; Gratz & Roemer), when characterizing our sample as being individuals who have problems regulating emotions. The mean DERS total score across all published reports (n = 13) with adult psychiatric samples (n = 19) is 112.15 (SD = 22.38). Following the established protocols from previous studies, we will use a total score of 90 or higher in the DERS for inclusion. In our previous study (Pro000035922), the 208 eligible participants had a mean DERS score of 117.6 (SD=17.95) at intake. These participants met criteria for a variety of affective and personality disorders, including major depression (68.3%, 22.1% current), generalized anxiety disorder (40.4%), and borderline personality disorder (11.1%). Therefore, we are confident that this DERS threshold will ensure recruitment of a transdiagnostic, clinical sample with emotion dysregulation.

Exclusion criteria include

- (1) Current mania;
- (2) Meets criteria for any current psychotic disorder symptom;
- (3) Currently/chronically homeless;
- (4) Current suicidal ideation (see data & safety section for specific criteria);
- (5) Psychiatric hospitalization within past 6 months;

(6) Unable to read, blind or deaf. Our previous study recruited only participants who were currently in treatment, but this study will include both participants who are currently in treatment, as well as those who are not in treatment. Intelligence Quotient (IQ) will be assessed with the North American Adult Reading Test (NART). 21-22 Subjects with a NART calculated IQ score of <90 will be excluded from the study.

(7) high self-reported autistic traits, as assessed by the Autism Spectrum Quotient (Auyeung & Baron-Cohen, 2012). If participants score more than 6 out of 10 for the total score, they are considered at risk for autism.

**Clinical Assessment.** Individuals not excluded by the phone screen will come to the lab to determine eligibility for the study. Upon arrival, a Clinical Assessor will review the consent form, answer any questions, and obtain written informed consent. Next, the Clinical Assessor will administer diagnostic interviews (SCID I, II for DSM-5) and self-report instruments (i.e., demographics, DERS) needed to assess all other inclusion/exclusion criteria. Ineligible participants will be debriefed and compensated (\$10) for their partial participation. Eligible participants will complete remaining assessments. This approach helps to reduce unnecessary participant burden and increase project efficiency. After inclusion/exclusion criteria are assessed and eligibility is confirmed, participants will schedule their next appointment (ideally min 1 day and max 14 days post screening). Of note, the population being seen in this study can have many different problems currently and in their past and sometimes the interview assessments, along with assessing inclusion/exclusion criteria, can last longer than expected. At the subject's discretion, we may have to finish portions of the assessment interviews (non inclusion/exclusion portions) on a second day. If that is the case, the subject will finish the interviews or the self-report scales on a separate day or on Day 1 of the experiment, after the computer experiment.

Participants who are unable to return, unexpectedly for the training session within 14 days of the last day of the assessment (due to reasons such as sickness, holidays, weather related incidents, unexpected travel or transportation issues), but who remain in contact with the coordinator and are still willing and able to come in to complete the study, will be allowed to continue in the study. The assessor who collected their personalized scripts will check in with the subject prior to the training session to verify that the scripts are still valid stressors. If the training session visit occurs within one month of the screening assessment, all SCID-I & SCID-II data collected from assessment will still be valid (as per the SCID assessment standards). If the training session visit occurs more than one month after the assessment day, the subject will be rescreened (i.e. will sign another consent, redo DERS, all self-report, SCID-I, THI and scripts. We allow screen fail subjects who did not meet inclusion/exclusion criteria at the first visit to rescreen for the study, if it is deemed appropriate (examples include DERS<90).

